The cognitive reorientation intervention we have developed and pilot tested is a simple but potentially powerful strategy to provide structured information in a familiar voice to patients on a regular basis. Because the intervention has a strong nursing care focus, it has the potential to affect delirium in ways that are distinct from but synergistic with medical care, which has focused primarily on pharmacologic management of delirium. The FAVoR intervention we propose in this project holds promise for reducing delirium in critically ill adults, improving sleep in the ICU, and secondarily benefitting cognitive function post-ICU.

We will accomplish the objectives using a prospective, randomized, experimental design to achieve robust and unbiased results. Subjects (n=182) will be randomly assigned within 48 hours of ICU admission and intubation to one of two groups. In the intervention group, scripted audio messages recorded by the patient's family (FAVoR) will be played for the patient at hourly intervals during daytime hours. These messages will be personalized, delivered automatically, and provide information about the ICU environment. Subjects in the control group will not receive recorded audio FAVoR messages. The FAVoR intervention, a standardized protocol developed and tested in preliminary work, will be delivered by audio recording for 5 consecutive days (120 hours), or until ICU discharge if discharge occurs within the first 5 days. The number of episodes of delirium during ICU stay is the primary outcome measure. We will also collect data at 1 month and 6 months following ICU stay for secondary aim 3. A model of the study is presented in Figure 1.

IRB Study Number: 20170771, Version #1.8, Date: 03/10/21, PI: [name]

[figure not shown]
Preliminary Studies

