2. Reorientation Intervention for Cognitive Dysfunction in the Critically Ill: A Feasibility Study. We conducted a randomized, controlled, preliminary study to explore the effect of a cognitive reorientation intervention on delirium in a small sample (n=30) of critically ill adults. Thirty adult patients admitted to Tampa General Hospital ICUs were randomized to three groups. The sample was 63% male, ranged in age from 19 to 97 years old (mean 59.5, SD 17.0), and had a mean APACHE severity of illness score of 64 (SD 20.7). Using scripts developed in preliminary study 1, ten subjects were randomized to receive automated, scripted reorientation messages in a familial voice, ten subjects received the same messages in a nonfamilial voice (bilingual female research team member) and ten subjects did not receive a reorientation message. Delirium was evaluated by the Confusion Assessment Method (CAM)–modified ICU version. The family voice group had more delirium free days than the non-familial voice group, and significantly more delirium free days (Chi-Square, $p= 0.0450$) than the control group (see figure 2). During the three-day intervention period, mean days of delirium were 0.2 in the family voice group, 0.8 in the staff voice group, and 0.9 in the control group. Wrist actigraphy was recorded for a maximum of three consecutive days starting from the time of admission to the ICU. Actigraphy was successfully obtained in 76% (n=23) of the sample. Sleep efficiency was calculated from actigraphy data to evaluate sleep in the ICU. To explore the possible mediation effect of sleep in a longitudinal study setting, we fitted two linear mixed models: (1) the ICU-CAM score against the group assignment and (2) the ICU-CAM scores against the percent of sleep and Sobel's test was applied. Following the reorientation intervention, sleep efficiency increased from baseline in both intervention groups, but decreased in the control group. The mean sleep efficiency in the family voice group increased from 56% to 66%, and sleep efficiency also increased from 45% to 52% in the non-familial voice group, both compared with the control group (sleep efficiency decreased from 54% to 52%). While it was not statistically significant, there was a trend towards improvement of the sleep efficiency as measured by actigraphy in the two intervention groups. Based on the results of the preliminary study that indicated family voice was most effective, we focused the primary aim of this proposal on testing the effect of family voice on delirium.

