- 1) **Intervention Group:** Subjects in the intervention group will receive personalized digitally recorded reorientation messages administered for up to 2 minutes every hour over an 8-hour daytime period (beginning at 9 am daily) recorded in the voice of a family member. Subjects in the intervention group will continue to receive the intervention for up to a total of 5 days (120 hours), or until ICU discharge if ICU discharge occurs within the first 5 days. Since in the ICU setting delirium has a mean onset of 2.6 days (S.D. +/- 1.7), and a mean duration of 3.4 +/- 1.9 days,⁴⁹ a 5-day period for the study intervention is appropriate and includes the period prior to delirium onset as well as when delirium has been shown to occur most frequently.
- 2) **Control Group:** The control group will consist of usual care, and will not receive audio reorientation messages. Subjects will remain in the study for five days or until ICU discharge if discharged before five days.

Subjects in both groups will be reoriented by care providers as part of usual care practices. Data will be collected from the medical record daily. Both groups (intervention and control) will undergo longitudinal cognitive and patient-reported health status evaluations concurrently with 24-hour sleep profiler-polysomnography and actigraphy at three different points in time. The first time point is inpatient, at least 24 hours after ICU discharge, then outpatient with two home visit data collection events at 1 month and 6 months post hospital discharge.

Description of Intervention. The FAVoR intervention includes a set of 8 recorded messages which were developed in preliminary study 1, and were tested and refined in preliminary study 2. Based on the feasibility data (preliminary study 2) each message is scripted, is no longer than

IRB Study Number: 20170771, Version #1.8, Date: 03/10/21, PI: [name]

2 minutes long, is a personal message using the subject's name, uses simple terms, and is written at a 5th grade reading level. Messages include information about the critical care environment, the visual and auditory stimuli to be expected, and the availability of providers and family. The messages call the patient by name (preferred name as recommended by the patient's family); we believe the use of the patient's name may create greater attention to the message.

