3. SP-PSG (substituted by PROMIS-SD and PROMIS-SRI)
4. NIH Toolbox Cognition Battery (substituted by PROMIS-CF and PROMIS-CFA)

Delirium. The primary outcome measure for this project is delirium free days. We will quantify delirium using the Confusion Assessment Method for the ICU (CAM-ICU).⁴⁵ CAM-ICU scores for each subject will be obtained by study personnel twice daily at 9 am and 4 pm (coinciding with the schedule for initiation and conclusion of messages each day in the FAVoR intervention group, and at identical times for the control group). CAM-ICU scores will also be recorded at the same times for two days following the completion of the intervention period. The Confusion Assessment Method (CAM) will be used during study visits after transfer from the ICU (post ICU, 1 month, and 6 month follow up periods) for comparison.

We will also collect documentation by providers in the medical record of episodes of delirium occurring outside of the CAM-ICU data collection conducted by research personnel. Only days without any instances of delirium will be counted as delirium free days. The CAM-ICU is recognized in the Clinical Practice Guidelines for the Management of Pain, Agitation, and Delirium in Adult Patients in the Intensive Care Unit as a valid, reliable, and feasible tool to detect delirium in ICU patients³ with pooled sensitivity of 75.5% and specificity of 95.8%.⁵⁰

Sleep/Activity. Sleep patterns in the critically ill are highly disorganized, with fragmentation, a predominance of light sleep, and reduction in deep sleep and rapid eye movements.⁸ We will use the FDA approved Sleep Profiler system (Advanced Brain Monitoring, Carlsbad, CA) to obtain continuous polysomnography data (SPPSG). The Sleep Profiler has been successfully utilized in mechanically ventilated and sedated patients and provides three frontopolar electroencephalographic (EEG) signals (AF7/AF8, AF7/Fpz and AF8/Fpz).⁵¹⁻⁵⁴

A wrist actigraph (ActiWatch Spectrum, Philips Respironics, Bend, OR) will be placed on the wrist to measure patient activity and ambient light levels. We have extensive experience with

IRB Study Number: 20170771, Version #1.8, Date: 03/10/21, PI: [name]

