There will be two parts of the data analysis: Part I: A traditional statistical data analysis for randomized controlled trials for the Primary Specific Aim, and Part II: Pathway analytic model analyses to address the secondary aims. [name] will work closely with the Data Manager to perform all the planned data analyses for this study.

Part I: We will follow the research and regulatory guidelines for statistical analysis of clinical trials including the ICH Guideline⁷⁷ and the CONSORT guidelines⁷⁸. First, descriptive statistics will be performed to describe and compare the characteristics of the intervention and the control groups. Descriptive statistics will be reported as means +/- standard deviation for continuous variables and as frequencies and percentages for categorical variables. Shapes of the data distributions, missing data and outliers will be examined by both graphics and statistical tests. Any data issues identified will be discussed with the PI and other investigators and addressed before formal data analysis. For example, skewed variables may be transformed so that their distributions are close to the Normal Distribution. Outliers may be excluded or included in two separate analyses. Missing data may be imputed or handled by other missing data techniques. Distributions of continuous variables and categorical variables will be compared between the intervention and the control group by using the t-test or Wilcoxon rank sum test and the Chisquare test, respectively. Any baseline covariate that is differentially distributed in the two groups will be adjusted in the subsequent analysis for testing the intervention effect. Assuming the randomization produces well balanced intervention and control groups, a Chi-square test for a 2x2 table with the number of delirium free days and the treatment assignment will be performed to test the primary hypothesis. If there are unbalanced covariates, then covariance adjustment will be performed by using logistic regression that includes both the treatment assignment and the unbalanced covariates. If there are missing values in the primary outcome, then multiple imputation will be performed using SAS PROC MI for missing at random (MAR) data.^{79,80} Sensitivity analysis for potentially not missing at random data will be performed using the Yau and Little⁸¹ Intent-to-Treat Analysis for Longitudinal Studies with Dropouts.

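### The primary 2x2 chi-square on delirium free days does not make the patient the unit of analysis; if patient-days are pooled, as a literal reading implies, type I error is roughly 15-28% rather than 5%

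*Combined protocol and SAP*

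**What the plan says.** Section 10, Part I, states that "a Chi-square test for a 2x2 table with the number of delirium free days and the treatment assignment will be performed to test the primary" question. If baseline covariates differ between arms, "covariance adjustment will be performed by using logistic regression that includes both the treatment assignment and the unbalanced covariates". Neither sentence names the row unit, a cut point or a clustering term.

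Section 9 (Key Variables, Delirium) states: "The primary outcome measure for this project is delirium free days". It classifies each day: "Only days without any instances of delirium will be counted as delirium free days". CAM-ICU is taken twice daily during the intervention period of up to five days and for two days afterwards. Section 4 names a different primary outcome: "The number of episodes of delirium during ICU stay is the primary outcome measure".

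Two other places bear on the unit. Section 8 sizes the trial in subjects: 182, or 91 per group, for a chi-square test with 2 degrees of freedom, W = 0.35, alpha 0.05 and 95% power. Section 4 (Preliminary Studies, study 2) reports that the family voice group had "significantly more delirium free days (Chi-Square, $p= 0.0450$) than the control group", and that "mean days of delirium were 0.2 in the family voice group, 0.8 in the staff voice group, and 0.9 in the control group" over a three-day period with ten patients per group.

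On the course of delirium, Section 9 (Group Assignment) says "delirium has a mean onset of 2.6 days (S.D. +/- 1.7), and a mean duration of 3.4 +/- 1.9 days", and Section 4 puts incidence at up to 80% of ventilated patients.

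**The concern.** A per-patient count of delirium free days runs from 0 to 5 (or 0 to 7). It fits two columns only if it is cut somewhere, and no cut is given. A table of days, free or not free, by arm is the only 2x2 table on this outcome that needs no unstated rule. In that table one patient contributes several entries.

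The chi-square reference distribution assumes independent entries. Delirium comes in spells of several days, and some patients never have it, so days from one patient resemble each other. The test would then understate its standard error and reject too often even if the intervention did nothing. An ordinary logistic regression with days as rows would share the fault. This is the only primary test, so the trial's main conclusion is at stake.

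**Working it through.** **1. What the sample size counts.** For a chi-square test with noncentrality N × W², W = 0.35, alpha 0.05 and 95% power, 2 df needs N = 127. Inflating for 40% attrition gives 127 × 1.4 = 178 or 127 / 0.6 = 212. With 1 df, N = 107 and 107 / 0.6 = 179. None equals 182, but 178 and 179 are within 3% of it, so the calculation was made in subjects. It does not settle the unit of the test, because a 2x2 table has 1 df and Section 8 uses 2.

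**2. The pilot p-value.** If all days were observed, each arm has 10 × 3 = 30 patient-days. Means of 0.2 and 0.9 are then 2/30 and 9/30 delirium days. For the table (2, 28; 9, 21):

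- Uncorrected: 60 × 210² / (11 × 49 × 30 × 30) = 5.45, p = 0.0195.
- Continuity-corrected: 60 × (210 − 30)² / (11 × 49 × 30 × 30) = 4.01, p = 0.0453.
- Fisher's exact test: p = 0.0419.

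The reported value is 0.0450. There are 24 pairs of patient-level 0-3 day distributions with totals 2 and 9. Over all of them, the nearest Pearson chi-square on patients gives p = 0.0510 (for example 1/10 against 5/10 with any delirium). A likelihood-ratio chi-square on that same table gives 0.0437.

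**3. Size of the inflation if days are pooled.** With m days per patient and intraclass correlation ICC, the design effect is DE = 1 + (m − 1) × ICC. The actual type I error is about 2 × [1 − Φ(1.96 / √DE)]. For example:

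- m = 5, ICC 0.3: DE = 2.2, error 18.6%.
- m = 5, ICC 0.5: DE = 3.0, error 25.8%.
- m = 7, ICC 0.2: DE = 2.2, error 18.6%.

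The documents give no ICC, so it was derived by simulating trials with no effect. Inputs from the plan: 91 per arm, onset 2.6 (SD 1.7) days, duration 3.4 (SD 1.9) days. Assumptions: one spell per patient, gamma-shaped onset and duration, and incidence of 40-80%, of which only the upper figure is in the plan. Results for full stays, 3,000 trials each:

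| Window | Incidence | ICC | Pooled days | One yes/no per patient |
|---|---|---|---|---|
| 5 days | 40% | 0.446 | 25.2% | 5.3% |
| 5 days | 60% | 0.376 | 22.5% | 4.7% |
| 5 days | 80% | 0.268 | 18.6% | 5.2% |
| 7 days | 40% | 0.365 | 27.8% | 4.7% |
| 7 days | 60% | 0.294 | 24.6% | 4.9% |
| 7 days | 80% | 0.208 | 19.4% | 5.0% |

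Allowing early ICU discharge takes the lowest pooled figure to 16.5%. Runs with lognormal shapes take it to about 15%. A patient-clustered test rejects in 4.7-5.8%. One dichotomised value per patient (any delirium, or a median split) rejects in 4.0-5.8% over all scenarios.

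**The case against.** The best defence is that nothing in the documents says days are pooled. The sample size is in subjects, the hypothesis is about subjects, and the outcome is naturally one count per subject. Dichotomise that count and alpha holds. The team also models repeated measures elsewhere: linear mixed models in the pilot and a multilevel structural equation model for secondary aim 1. All of this stands, and it makes the inflation conditional. It does not remove the gap, because the patient-level reading needs a cut that the plan never gives.

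A reader might infer from the pilot that the team certainly pools days. The documents do not support that. The match is 0.0453 against 0.0450, not exact, and it assumes that all 30 days per arm were observed, which is not stated. A patient-level likelihood-ratio test comes about as close as the Fisher test on days. If the p-value came from all three arms, patient-level Pearson tests can give 0.0449 or 0.0451, although the sentence reads as a two-arm comparison. The pilot is suggestive only, and it would not fix the unit in Section 10 in any case.

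The simulation also rests on spell shape, one spell per patient and a lower incidence bound that the plan does not give.

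**Conclusion.** The point holds as an under-specified primary test with a serious consequence under its most literal reading. If patient-days are pooled without clustering, type I error is roughly 15-28% against the stated 5%, or about three to five times too high. This assumes one gamma or lognormal spell per patient with the plan's onset and duration, and 40-80% incidence. If each patient is dichotomised, alpha is near 5%, but the cut is left open and the count loses information. The logistic fallback has the same ambiguity.

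A reader might go further and say that the plan treats each patient-day as an independent subject and that its true error rate is 16-28%. The documents do not support this as fact, because the unit is simply not stated. The correction is still needed before analysis: nothing in the plan prevents pooling, and a patient-level method is better than the stated test on either reading.

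**What to change.** In Section 10, Part I, state that the randomised patient is the unit of inference. Replace the 2x2 chi-square and ordinary logistic regression with one analysis of delirium free days out of assessed days. This can be a binomial or logistic GEE clustered by patient with robust standard errors, or a test that permutes arm by patient. Use the same clustered model for any covariate adjustment. State the window (five or seven days) and what counts as an assessed day. Reconcile the outcome with the episode count named in Section 4, and the test with the 2 df power statement in Section 8.

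In Section 4, study 2, state the unit of the pilot chi-square. If it was patient-days, give the patient-level p-value. If all days were observed, a patient-level permutation test gives p between 0.006 and 0.25 over the 24 compatible data sets, and above 0.05 in 19 of them, so the figure must come from the pilot data.

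The cost is wording and a few lines of code, with no extra patients or data. The downside is a wider interval than pooled days would give, but a valid one. If the team already intended a patient-level test, the change only makes that explicit and avoids an arbitrary cut.

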	Drug type and cumulative sedative dose	**	**	**	**	**	***	***
	APACHE IV STOP-BANG SOFA			**	*		***	***
	Age, sex, race/ethnicity		*		**	**		
Patient-reported Health Status	PROMIS Global Health					*	***	***
Patient-reported Sleep Quality	PROMIS-SD PROMIS-SRI					*	***	***
Patient-reported Cognitive Function	PROMIS-CF PROMIS-CFA					*	***	***
Cognitive Function	NIH Toolbox Cognition Battery					*	*	*

Note:

* = Data collection in person (measures shaded in grey are temporarily paused)

** = Data collection from the electronic medical record

*** = Data collection via telephone or video conference visit (measures highlighted in yellow are telephone- or video-collected substitutes for in-person visits)

We plan to review approximately 350 medical records in order to achieve our sample size of 182 enrollments during the 4-year study. The data collection schedule is shown in Table 2.

IRB Study Number: 20170771, Version #1.8, Date: 03/10/21, PI: [name]

Table 2. Study Timeline

Activity	Year	Year 1			Year 2			Year 3			Year 4		
	Months	1-4	5-8	9-12	1-4	5-8	9-12	1-4	5-8	9-12	1-4	5-8	9-12
Hire/train personnel													
Database refinement													
Subject recruitment and enrollment													
Subject 1 and 6 month follow up													
Data collection													
Data management													
Analysis of final results													
Final results manuscript													
Final grant report													

8. Study Endpoints

Primary Endpoint. To test the effect of the Family Automated Voice Reorientation (FAVoR) intervention on delirium in critically ill, mechanically ventilated adults during hospitalization in the ICU, we plan for 95% power respectively to detect an effect size (W) of 0.35 using a 2 degrees of freedom Chi-Square Test with a significance level (alpha) of 0.05.

Secondary Endpoint. The recently completed BRAIN-ICU descriptive study of ICU survivors reported a 43% attrition from the inpatient sample to a 12 month follow up time point.¹⁸ Given that a secondary aim of the proposed project plans 1month and 6 months post-hospital discharge follow up, we conservatively planned for a 40% attrition rate, which is a sample size of 182 total (91 in each group).

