All data will be downloaded into research electronic data capture (REDCap), a secure web application database, which will be accessed by a secure UM web connection with authentication and data logging. The Project Director will review all data for completeness and appropriate entries before it is entered into the study database. At the beginning of the data entry process a minimum of 1 in every 10 participant records will be checked against the original medical record for data errors. Records for review will be randomly chosen by the data manager. As the study progresses, the frequency of monitoring will be based on the results of the previous data review. If the error rate is unacceptable then the monitoring will increase until the error rate is acceptable (less than 5% of all data). The Data Manager in consultation with the Principal Investigator will develop reports that will help in the coordination and management of the project and also allow project staff to monitor the quality of the data and the progress of the study. Furthermore, only a unique identifier, assigned by the Principal Investigator or Data Manager, in the database will identify each subject. The data files will be backed up daily during the data entry process and once a week during other times by the Project Director. All data files will be housed on the university server which is backed up every 24 hours and copies are stored off-site for additional security. Access to the database will be password protected and limited to the investigators, Project Director, and Data Manager.

Data Analysis Plan

The primary specific aim of the proposed project is to test the effect of the Family Automated Voice Reorientation (FAVoR) intervention on delirium in critically ill, mechanically ventilated adults during hospitalization in the ICU. We hypothesize that subjects who receive the FAVoR intervention will have less delirium than control subjects who do not receive the intervention.

Secondary aims of this project are to: (1) explore if the effect of FAVoR on delirium is mediated by sleep, (2) explore if selected biobehavioral factors may potentially moderate the effects of FAVoR on delirium, and (3) examine the effects of FAVoR on short term (immediately after ICU discharge) and long term (1 and 6 months after hospital discharge) outcomes, including cognitive function and patient-reported health status.

IRB Study Number: 20170771, Version #1.8, Date: 03/10/21, PI: [name]

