Part II: Given the large number of variables measured for activity/sleep, disease severity, environment and demographics and the potential complex pathways among these variables, we plan to use partial least square structural equation models (PLS-SEM) to analyze the relative importance and the pathways of these variables.

Partial least squares (PLS) is a predictive modeling method that can predict high dimensional outcomes from high dimensional, correlated predictors. The variance importance in projection (VIP) measure in PLS models can be used to compare the relative importance of different predictors which is a useful tool for variable selection in high dimensional data.⁸² In recent years, PLS-SEM was developed to use PLS fit pathway models with both manifested and latent variables.⁸³⁻⁸⁶ PLS-SEM is implemented in the R package semPLS. We will perform the predictive PLS using SAS PROC PLS for variable screening so that important predictors from the high dimensional raw data (such as the sleep measure) will be identified. Then we will fit PLS-SEM using the R package semPLS to the mediation effect of sleep and other empirically or theoretically hypothesized pathways. Specifically, for secondary aim 1, we will perform mediation analysis within multilevel SEM; for secondary aim 2, we will test moderation in PLSSEM to test the biobehavioral factors as multiple moderators; and for secondary aim 3, we will fit path analytic models from the FAVoR intervention to the short-term and the long term cognitive function and patient-reported health status measures, respectively.

IRB Study Number: 20170771, Version #1.8, Date: 03/10/21, PI: [name]

11. Provisions to Monitor the Data to Ensure the Safety of Subjects

In addition to the Data Safety and Monitoring plan described below, the study will be monitored under the quality assurance procedures of the SONHS which includes a review of the regulatory binder, review of consents upon enrollment of the first 5 participants and every 6 months thereafter until human subjects activities are completed.

Data Safety and Monitoring Plan

Purpose:

The purpose of the DSM Plan is to:

1. Assure monitoring of the progress of the trial and the safety of participants
2. Assure compliance with reporting requirements for adverse events
3. Assure data accuracy and protocol compliance.

Required elements:

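### Part II screens sleep variables with PLS and fits the mediation model to the same sample, with nothing that carries the selection into inference on the sleep-to-delirium path

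*Combined protocol and SAP*

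**What the plan says.** The analysis of the secondary aims is in the Combined protocol and SAP, section 10 (Data Management), Data Analysis Plan, Part II. The stated motive is dimension: "Given the large number of variables measured for activity/sleep, disease severity, environment and demographics". The plan introduces the VIP measure from PLS as a way to compare predictors, "which is a useful tool for variable selection in high dimensional data", and then sets out two steps in order.

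- Screening: "We will perform the predictive PLS using SAS PROC PLS for variable screening so that important predictors from the high dimensional raw data" are identified. The sleep data are the example given.
- Modelling: "Then we will fit PLS-SEM using the R package semPLS to the mediation effect of sleep", along with other pathways hypothesised on empirical or theoretical grounds.

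For aim 1 the mediation analysis is placed within a multilevel SEM. For aim 2, "we will test moderation in PLSSEM to test the biobehavioral factors as multiple moderators". For aim 3, path models run from FAVoR to cognition and health status.

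Part II does not name the response used in the screen, a VIP cut-off, the number of components, or how p-values and intervals will be obtained. It mentions no sample split, hold-out, cross-validation, post-selection method or multiplicity rule. Only one sample appears in the document, the 182 subjects. Aim 1 is worded as exploratory: "explore if the effect of FAVoR on delirium is mediated by sleep".

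**The concern.** Predictive PLS is supervised: it ranks candidates by how well they predict a response. If that response is delirium, the sleep measures that reach the mediation model are the ones whose sample association with delirium was largest. A test of that association on the same subjects, as if the measures had been named beforehand, rejects a true null more often than its nominal level, and its interval is too narrow.

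Mediation needs two links, FAVoR to sleep and sleep to delirium. Screening weakens the protection on the second. If FAVoR changes sleep broadly but sleep has no bearing on delirium, the trial could report a sleep pathway that does not exist. The exploratory label limits how strongly such a result may be stated, but it does not correct a p-value or interval that is printed.

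**Working it through.** The plan gives no error rate, number of candidates or alpha for Part II, so there is no stated figure to reproduce. The check is a null calculation under stated assumptions.

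**Inputs**

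- Sample: 182 (91 per arm). As a low case, 109, from "we conservatively planned for a 40% attrition rate, which is a sample size of 182 total (91 in each group"): 182 × 0.6 = 109.2.
- Level: 5%. The plan states 0.05 for the primary test only, so its use here is assumed.
- Assumed: 5, 10, 20 or 40 candidate sleep measures; common correlation 0, 0.3 or 0.5; screening response delirium, simulated as one continuous value per subject; one-component PLS; keep if VIP > 1.
- No true link between sleep and delirium.

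**Step 1. Each measure kept by VIP > 1.** With one component and K candidates, VIP_j = √K × |w_j|, where the weights w are proportional to the correlations with the response and scaled to length 1. So VIP_j > 1 means that the measure's squared correlation exceeds the average. With many independent null measures this is close to |z| > 1, which has probability 0.317. Nearly all measures with p < 0.05 pass, so the rejection rate among those kept is about 0.05 / 0.317 = 15.8%. Simulation (3,000 runs per setting, n = 182 and 109, correlations 0 and 0.5) gave 11.5% to 15.6%, against 4.8% to 5.3% without screening. At correlation 0.3 the rate is about 12-15%. An equal-weight composite of the kept measures was significant in 19% to 33% of runs, against 4.3% to 5.9% unscreened.

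**Step 2. Top-ranked measure only (upper case).** For independent measures the rate is 1 − 0.95^K. Simulated rates at n = 182:

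| K | 1 − 0.95^K | corr. 0 | corr. 0.3 | corr. 0.5 |
|---|---|---|---|---|
| 5 | 22.6% | 22.6% | 20.0% | 17.0% |
| 10 | 40.1% | 40.6% | 36.1% | 28.6% |
| 20 | 64.2% | 63.9% | 53.9% | 42.8% |
| 40 | 87.1% | 86.9% | 74.8% | 57.4% |

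With n = 109 and correlation 0.3 the rates were 22%, 35%, 54% and 74%, so sample size hardly matters.

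**Step 3. False mediation through the top-ranked measure.** Both links must be significant. A 0.6 SD shift with 91 per arm has expected z = 0.6 × √(91/2) = 4.05, so power is about Φ(4.05 − 1.96) = 0.98. At correlation 0.3:

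- FAVoR shifts one measure of K. That measure is top-ranked with probability 1/K. Otherwise the FAVoR-to-sleep link is significant by chance, 5%. The approximate rate is (Step 2 rate) × (0.98/K + 0.05 × (K − 1)/K).
 - K = 5: 0.200 × 0.236 = 4.7%.
 - K = 10: 0.361 × 0.143 = 5.2%.
 - K = 20: 0.539 × 0.0965 = 5.2%.
 - K = 40: 0.748 × 0.0733 = 5.5%.
 - Simulation (300 runs each) gave 4.7%, 7.0%, 4.7% and 4.0%, with Monte Carlo error √(0.05 × 0.95/300) = 1.3 points.
- FAVoR shifts every measure. The rate is about 0.98 × 0.200 = 19.6% at K = 5 and 0.98 × 0.748 = 73.3% at K = 40. Simulations gave 22% to 72% and, in a repeat, 20% to 67%.
- One measure named in advance gave 3.6% to 6.2% (correlations 0 and 0.5).

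**Step 4. Paths that are not inflated.** With screening on the outcome, the FAVoR-to-sleep path rejected in 4.5% to 5.8% of null runs and the treatment-by-measure interaction in 4.7% to 5.7%. Aim 3 paths start from the randomised arm, which is not a screened variable; this follows by reasoning and was not simulated.

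**Step 5. Does resampling the screen repair it?** With 400 data sets of n = 182 and 400 resamples each, a bootstrap that held the selected measure fixed excluded zero in 26.5% (K = 5) and 59.5% (K = 20) of null data sets. Repeating the screen in each resample cut this to 3.8% and 1.5%. A separate check moved from 28-57% to 3-4%.

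**The case against.** The strongest reply is that the plan is silent rather than wrong. Part II never says that the PLS response is delirium, that a single best variable will be tested, or that p-values will be computed as if no screen had taken place. It speaks of important predictors in the plural, of latent variables, and of pathways hypothesised in advance, which need not be selected from the data. Aims 1 and 2 are exploratory and the primary test is separate.

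Most of this stands, and it sets the scope. That the same subjects are used and the selection ignored is inferred from silence, although the document contains no second data set. The 20-75% figures describe a best-of-K choice that the plan does not announce; the VIP > 1 figures are nearer to what it describes.

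Two stronger readings are tempting and are not supported:

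- A reader might infer that false mediation by sleep would be reported in up to three quarters of trials. That takes the one-path upper case for the two-path result. When FAVoR moves a single measure, the false mediation rate stays near 5%. The high rates need FAVoR to move all candidates substantially. The document does not show this: the pilot's sleep-efficiency trend was not statistically significant.
- A reader might infer that every Part II result is compromised. Step 4 shows otherwise for the FAVoR-to-sleep path and the aim 2 interactions under outcome-based screening, and aim 3 does not start from a screened variable.

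What does not stand is the view that the exploratory label disposes of the matter. The plan says that it will test moderation and analyse mediation, and it intends to publish. Nothing says that screened paths will appear without p-values or intervals.

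**Conclusion.** The point holds for one path in aim 1: from a screened sleep measure to delirium, if delirium is the screening response. Naive inference there is too optimistic, at about 12-15% instead of 5% per VIP-selected measure, rising to 20-75% if only the top-ranked measure is carried forward. False mediation through the top-ranked measure lies between about 5% and about 70%, depending mainly on how many sleep measures FAVoR shifts.

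These sizes rest on assumed candidate numbers (5 to 40), correlation (0.3), cut-off (VIP > 1) and shift (0.6 SD), none of which is in the plan, and on a simplified outcome with one value per subject. The direction does not depend on them: inflation is clear with five candidates. A different screening response would move the problem to the paths into that response, which is one more reason to name it. The primary analysis is untouched. This is a minor improvement to an exploratory analysis.

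**What to change.** In Part II, state that intervals for any path starting from a screened variable will come from a bootstrap in which the whole PLS screen is repeated in every resample. Whole subjects should be resampled so that repeated days stay together. For this to be reproducible, also state the screening response, the number of components, the VIP cut-off, and how a resample that drops a measure is counted. Where this is not done, report those paths as hypothesis-generating, without p-values.

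The cost is SAP wording, computing time and wider intervals. In the check above the method was somewhat conservative (1.5% to 3.8% against 5%). Screening on one half and testing on the other also restored the level (4.4% to 6.2% for the top-ranked measure), but leaves only 91 of 182 subjects for the test.

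Naming one sleep measure in advance is an option for the investigators, not a required change. Sleep efficiency has a precedent in the pilot: "Sleep efficiency was calculated from actigraphy data to evaluate sleep in the ICU". But pilot actigraphy was obtained in only 76% of subjects, and this trial adds polysomnography. A single named measure would need its device stated, and an actigraphy measure would give up the polysomnography measures as mediators.
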